## List of Abbreviations

3D CRT	3 Dimension Conformal External Beam Radiation Therapy
5-FU	5-fluorouracil
AE	Adverse Event
CR	Complete Response
CT Scan	Computed Tomography Scan
CTCAE	Common Terminology Criteria for Adverse Events
CTV	Clinical Treatment Volume
CXR	Chest X-Ray
DSMC	Data Safety Monitoring Committee
EBRT	External Beam Radiation Therapy
ECOG	Eastern Cooperative Oncology Group
FACT-G	Functional Assessment of Cancer Therapy - General
FDG-PET/CT	[18F]-flourodeoxyglucose Positron Emissions Tomography / Computed Tomography
Fx	Fraction
Gy	Gray
LPFS	Local Progression-Free Survival
MD	Maximum Dose
OS	Overall Survival
PD	Prescription Dose
PD	Progressive Disease
PET/CT	Positron Emissions Tomography / Computed Tomography
PIV	Prescription Isodose Volume
PIV/TV	Prescription Isodose Volume/Tumor Volume
PTV	Planning Target Volume
QOL	Quality of Life
RT	Radiation Therapy
RTOG	Radiation Therapy Oncology Group
SD	Stable Disease
SBRT	Stereotactic Body Radiotherapy
TTP	Time to Progression
TV	Tumor Volume
WOOCBP	Women of Child-Bearing Potential

## **PROTOCOL SUMMARY**

### **Title**

**Stereotactic Body Radiotherapy (SBRT) for close or positive margins following resection of pancreatic adenocarcinoma**

### **Objectives**

The *primary* objectives of this study are to:

1. To determine the rate of local progression-free survival (LPFS) achieved in subjects with close (<2.5 mm) or positive margins after pancreatic cancer resection treated with SBRT

The *secondary* objectives of this study are to:

1. To determine the time to progression (TTP) and overall survival (OS)
2. To evaluate the acute and late toxicities associated with SBRT in this patient population
3. To evaluate quality of life (QOL) of locally-advanced pancreatic cancer subjects treated adjuvantly with SBRT

### **Subject population**

Subjects with primary adenocarcinoma of the pancreas that has been resected with positive margins or close margins (<2.5 mm)

Specific inclusion and exclusion criteria are detailed in Section 4.0

### **Number of subjects**

50

### **Study design and methodology**

This is a phase II study.

### **Treatments administered**

12 Gy x 3 fractions (36 Gy total)

### **Efficacy data collected**

The following evaluations will be conducted to assess the efficacy of SBRT:

- Local progression-free survival (LPFS)
- Locoregional and distant control
- Time-to-progression (TTP)

### **Safety data collected**

The following evaluations will be conducted to assess the safety of SBRT:

- Recording of all toxicity data per NCI CTCAE version 4.0
- Functional Assessment of Cancer Therapy – General (FACT-G)

## 1.0 BACKGROUND

### 1.1 *Adenocarcinoma of the pancreas*

Pancreatic cancer is the 4th leading cause of death from cancer of both men and women in the United States. There are expected to be 37,680 new cases and 34,290 deaths in the United States in 2008. Despite intensive research efforts into chemotherapy and radiotherapy, surgical resection remains the only treatment option associated with long-term survival. Unfortunately, pancreatic cancer is rarely resectable upon diagnosis, with approximately 40% presenting with locally-advanced but unresectable disease and an additional 40% presenting with metastatic disease. Within the United States, the 5-year survivals for local, locally-advanced and distant disease are 20%, 8% and 2% respectively, resulting in an overall 5-year survival for pancreatic cancer of only 5% (1). These values represent all pancreatic cancers. Adenocarcinoma of the pancreas, representing more than 90% of all cases, is believed to be the most aggressive malignancy with an even worse prognosis. For patients that are able to undergo surgical resection, the choice of adjuvant therapy remains controversial with data available for anything ranging from observation to chemoradiation.

### 1.2 *Radiation therapy as adjuvant treatment in pancreatic adenocarcinoma*

For many years chemoradiation was considered the standard of care after patients underwent resection of pancreatic carcinoma. This was mainly based on a small phase III randomized control trial by the Gastrointestinal Tumor Study Group (GITSG) (2). This trial randomized 43 patients to surgery with or without adjuvant 5-FU based chemoradiation. The radiation was delivered using outdated techniques (AP/PA and in a split course) to a total dose of 40 Gy. The patients in the experimental arm also received 2 years of adjuvant 5-FU. The experimental arm had a median OS of 20 months compared to 11 months in the control arm. Regardless, 50% of patients in both arms still developed local recurrence. There are also two large retrospective series from Johns Hopkins and the Mayo clinic. The JHU series contains over 600 patients, with 44% having received 5-FU based CRT to a median dose of 50 Gy. The other 44% did not receive adjuvant therapy. The CRT group had a median OS of 21.2 months compared to 14.4 months in the observation group (3). The Mayo series had 472 patients, all with an R0 resection. The median RT dose was 50.4 Gy and almost all patients received 5-FU. The median OS again favored CRT with a median OS of 25.2 months compared to 19.2 months in patients who were observed (4).

A few other studies have examined other adjuvant CRT regimens utilizing non-5-FU-based chemotherapy. RTOG 9704 compared gemcitabine to 5-FU before and after 5-FU based CRT. The study included 451 patients with gross total resection. The radiation dose was 50.4 Gy delivered using modern methods. There was a trend towards improved 3 year OS (31% vs. 22%) with the use of gemcitabine. Local recurrence remained a significant source of failure, but was lower compared to older studies at approximately 25%. Distant metastasis remained the most significant site of failure at greater than 70%, highlighting the importance of systemic therapy (5). The ACOSOG also published a small phase II trial of 89 patients with R0/1 resection of pancreatic head adenocarcinoma treated to 50.4 Gy along with chemotherapy. The chemotherapy was relatively intense, consisting of 5-FU, cisplatin, and alpha interferon and 96% of patients had grade 3 toxicity or greater. Despite such intense therapy local recurrence still remained around 50%, but systemic therapy only made up 35% of failures (6).

### 1.3 *Chemotherapy alone as adjuvant therapy*

There are a few key studies supporting the adjuvant use of chemotherapy alone after resection of pancreatic cancer. ESPAC-1 was a complex 2x2 factorial designed study with over 500 patients. The arms were 5-FU based CRT (split course technique), adjuvant 5-FU/leucovorin alone, both

CRT followed by chemo, or observation. For all patients, chemotherapy improved median survival from 14 months to 19.7 months. For patients that received chemotherapy the 5 year OS was 21% compared to 8%. When analyzing the effect of CRT, it appeared to have a detriment, with a 5 year OS of 10% compared to 20% when chemoradiation was not given. Drawbacks of this study include its complex design, use of outdated radiation techniques, lack of RT quality assurance, and the ability of treating physicians to give “background” therapy (7). The CONKO-001 study randomized 368 patients with a R0/R1 resection to observation of gemcitabine alone for 6 cycles. The use of adjuvant gemcitabine improved disease free survival from 7 months to 14 months, but not OS (22 months vs. 20 months) (8). There was also a metaanalysis published in 2005 examining outcomes of patients in randomized adjuvant trials. This study included 875 patients from 6 trials. The investigators found that chemotherapy improved median OS from 14 months to 19 months. Chemoradiation did not provide a statistically significant benefit (15.2 months to 15.8 months). Of interest, on subgroup analysis it was determined that CRT was more effective for patients with a positive margin resection (9).

### *1.3 Stereotactic body radiotherapy (SBRT)*

SBRT is technique that combines highly conformal radiotherapy with real-time imaging to deliver high doses of radiation in a small number of fractions. Modeled after intracranial stereotactic radiosurgery, SBRT has now been studied in a variety of extracranial locations including the spine, lung, liver, pancreas, and head and neck cancers. Because of the precise targeting, SBRT has the potential to improve upon the local control achieved with conventional EBRT while minimizing the dose to normal tissue. Most prospective randomized trials of conventionally fractionated EBRT for the treatment of locally-advanced pancreatic cancer have reported local control rates of 35%-55% (2-5). Koong, et al established the feasibility of using SBRT for locally-advanced pancreatic cancer in a phase I dose escalation study which achieved 100% local control with no treatment limiting toxicities at 25 Gy in a single fraction (10). A follow-up study combined conventionally fractionated 5-FU chemoradiotherapy with an SBRT boost resulting in 94% local control but no improvement in overall survival and an increase in toxicity compared to SBRT alone (11). A recent study combining full dose gemcitabine with single fraction SBRT reported 81% local control and 100% 1-year freedom from local progression. While acute toxicities were minimal, a significant number of subjects (47%) experienced Grade 2 or greater late toxicities, primarily duodenal ulcers (12). It is possible that these late toxicities may be reduced by increasing the degree of conformance of the radiation dose cloud and increasing the number of fractions, as studies comparing conventionally fractionated RT with hypofractionated RT have found an increased incidence of late GI toxicities in the hypofractionated group (13).

Another advantage to SBRT is the fractionation schedule. First, the entire course of treatment is often completed over 1 to 7 days versus the 5 to 8 weeks required for conventionally fractionated EBRT. Second, the accelerated fractionation schedule could improve overall survival by allowing earlier systemic doses of chemotherapy. Because pancreatic cancer is often characterized by progression to metastatic disease, early delivery of systemic chemotherapy is imperative to address potential sites of microscopic disease. In fact, some studies have evaluated the delivery of systemic chemotherapy followed by combined chemoradiotherapy for those subjects without evidence of disease progression. This strategy selects those subjects most likely to benefit from the local control provided by radiotherapy and in two separate studies has resulted in significant increases in TTP and OS for subjects treated with chemoradiotherapy compared to those receiving chemotherapy alone (14-15).

#### *1.3.1 Experience with SBRT at the University of Pittsburgh Cancer Institute*

A retrospective review from our institution evaluated the outcome in 71 subjects with intact pancreatic cancer treated with SBRT (16). With a median follow-up of 12.7 months the freedom from local progression at 6 months and 1 year was 72% and 49%, respectively. Median overall survival for the entire group was 10.3 months. Treatment-related toxicity was minimal with only 3 patients experiencing acute grade 3 toxicity (4%). There was no recorded late toxicity. We have been treating patients with close or positive margins with SBRT as well. We recently examined outcomes in 24 patients treated post-operatively with SBRT (17). Sixty-six percent of the patients had positive margins and the remainder had close margins of 1-2.5mm. The median follow-up was 1 year. The freedom from local progression at 6 months and 1 year was 95% and 66%. There was no acute or late grade 3-4 toxicity, and two patients (8%) had late grade 1-2 toxicity, again demonstrating that when done properly, SBRT has a low potential for toxicity. The current study seeks to further investigate the impact of SBRT following resection with a close or positive margin. We hope to improve local control, and through the use of a shortened treatment schedule, allow patients to begin systemic therapy earlier.

## **2.0 OBJECTIVES**

### *Primary*

2.1 To determine the rate of local progression-free survival (LPFS) with two years of follow-up in subjects with margin positive or close margins following resection of pancreatic adenocarcinoma treated with SBRT.

### *Secondary*

2.2 To determine the time to progression (TTP) and overall survival (OS) in this patient population

2.3 To evaluate the impact of SBRT on the QOL of subjects in the adjuvant setting

2.5 To evaluate the acute and late toxicities associated with SBRT for pancreas cancer

### 3.0 INVESTIGATIONAL PLAN

#### 3.1 Overall design and plan of the study

Detailed visit-by-visit study procedures and a study flow chart are provided in Section 6.0. Prior to enrollment, all subjects will be evaluated with physical examination, review of surgical pathology, discussion in a multi-disciplinary setting, review of imaging with the operating surgeon, and review of post operative imaging to establish the target volume.

#### 3.2 Radiation simulation

Contrast-enhanced CT based simulation will be obtained prior to any adjuvant treatment (2-4 weeks post-op depending on healing). The target volume will be identified based on fiducial marker placement at time of surgery as well as a detailed discussion and image review with the operating surgeon. This area will be contoured on axial CT images obtained at 1.25 mm slice thickness. These volumes will then be reconstructed into a 3-dimensional image set for SBRT planning. Subjects will be simulated in the treatment position (supine with arms raised) on the CT scanner table the appropriate immobilization. Optiray® contrast (125 mL Optiray 350; 350 mg/mL organically bound iodine; Ioversol; Mallinckrodt Inc., St. Louis, MO, USA) will be administered intravenously at a flow rate of 2.5 mL/s. A helical CT scan of the abdomen will be acquired with intravenous contrast starting 30 seconds prior to CT acquisition.

A 4D CT data acquisition for the same axial extent will be obtained. The images will then be electronically transferred from the CT workstation via DICOM3 to the appropriate treatment planning workstation in the department of radiation oncology. Based on axial CT images, fiducial marker placement, review of the pathology report, and a detailed discussion with the operating surgeon, contours will be drawn of the clinical target volume (CTV), which is defined as the area at risk for microscopic disease. The planning target volume (PTV) will be equivalent to the CTV unless motion is detected on the 4D motion study. If there is motion, the amount of motion in the superior-inferior, lateral, and anterior-posterior directions will be the margin given. Surrounding normal and critical structures will also be contoured by the treating radiation oncologist including the kidneys, liver, small bowel, spinal cord, and stomach if necessary.

#### 3.3 Stereotactic Body Radiotherapy Planning

An SBRT plan will be created by a medical physicist based on the PTV contoured on the CT scan. The plan will be to deliver fractionated SBRT to the isodose line best encompassing the PTV:

12 Gy x 3 fractions (36 Gy total)

In determining the radiation dose and fractionation scheme for this protocol, we used the linear-quadratic formalism for radiation cell killing to “equate” schemes that vary the dose/fraction and number of fractions. This concept of biologically equivalent dose (BED) states that the total effect is given by:

$$nd \times (1 + d/\alpha\beta)$$

where n is the # of fractions and d is the dose/fraction. The “alpha-beta ratio” characterizes the radiation response of a particular tissue; a higher value is indicative of a tissue that responds acutely to the effects of radiation. Due to their highly proliferative nature, most tumors fall into this category.

[figure not shown]
This dose scheme (36 Gy in 3 fractions) is biologically equivalent to the previously studied doses in the literature (24 Gy in 1 fraction). We would favor treating in three fractions, as opposed to one, to

allow more repair of normal tissue, reoxygenation of tumor cells, and redistribution of tumor cells to more radiosensitive parts of the cell cycle. Using a smaller fraction size, 12 Gy compared to 24 Gy, will also help reduce late effects of radiation therapy. SBRT treatment will be given on an every other day schedule, excluding weekends. The prescription dose will be prescribed to the isodose line best encompassing the planning target volume (PTV) depending on the volume of tumor.

Careful evaluation of each plan will be conducted by the radiosurgical team to ensure that normal tissues and critical structures tolerances are maintained.

The maximum dose (in Gy) within the treatment volume (MD), prescription dose (PD), and the ratio of MD/PD (as a measure of heterogeneity within the target volume), prescription isodose volume (PIV in  $\text{mm}^3$ ), tumor volume (TV in  $\text{mm}^3$ ), and the ratio of PIV/TV (as a measure of dose conformity of the treatment relative to the target) will be recorded. This concept is illustrated in **Figure 2**.

**Figure 2:** Example illustrating the concept of PIV/TV

### 3.4 Quality of Life Assessment

Quality of life assessment using the Functional Assessment of Cancer Therapy – General (FACT-G) tool, which is a validated tool, will be administered to all subjects prior to treatment and at each follow-up visit (Appendix A).

### 3.5 Treatment following SBRT

As described above, all patients will have been seen in a multi-disciplinary pancreatic cancer clinic. As such, they will be set up with a medical oncologist. Following completion of SBRT as described in this protocol, the patient's medical oncologist may, at his/her discretion, administer systemic therapy according to the current standard of care or the UPMC pathways.

## 4.0 SUBJECT SELECTION AND ELIGIBILITY

### 4.1 Selection of subjects

Enrollment is defined as the first day of protocol therapy.

#### 4.1.1 Number of subjects

50 patients will be enrolled to the study. The study has been designed to detect a 20% improvement in the rate of local progression-free response over that of historical controls.

#### 4.1.2 Inclusion criteria

Each subject must meet all of the following inclusion criteria to be enrolled in the study:

- Histologically or cytologically proven adenocarcinoma of the pancreas that has been resected with a close (<2.5mm) or positive margin based on surgical and pathological findings.
- Subjects will be staged according to the 2010 AJCC staging system (Appendix D) with pathologic stage T1-4, N0-1 being eligible; and have a primary tumor of the pancreas (i.e., pancreatic head, neck, uncinate process, body/tail)
- PTV must be encompassed in a reasonable SBRT “portal” as defined by the treating radiation oncologist
  - Karnofsky performance status  $\geq$  70 (ECOG 0-1)
  - Age  $\geq$  18
  - Estimated life expectancy > 12 weeks
- Patient must have adequate renal function as defined by serum creatinine < 2.5 mg/dl obtained within 28 days prior to registration
- Patient must have adequate hepatic function as defined by total bilirubin < 2.5 xIULN (institutional upper limit of normal) and either SGOT or SGPT < 3.0 xIULN, obtained within 28 days prior to registration.
- Patient must be able to swallow enteral medications. Patient must not require a feeding tube. Patient must not have intractable nausea or vomiting, GI tract disease resulting in an inability to take oral medication, malabsorption syndrome, or uncontrolled inflammatory bowel disease (Chron’s, ulcerative colitis).
- Ability to provide written informed consent
- Patient must not have uncontrolled intercurrent illness including, but not limited to, ongoing or active infection, symptomatic congestive heart failure, unstable angina pectoris, cardiac arrhythmia, history of myocardial infarction or cerebrovascular accident within 3 months prior to registration, uncontrolled diarrhea, or psychiatric illness/social situations that would limit compliance with study requirements.
- Patient must not be pregnant because of the risk of harm to the fetus. Nursing women may participate only if nursing is discontinued, due to the possibility of harm to nursing infants from the treatment regimen. Women/men of reproductive potential must agree to use an effective contraception method.

#### 4.1.3 Exclusion criteria

Subjects meeting any of the following exclusion criteria are not to be enrolled in the study:

- Non-adenocarcinomas, adenosquamous carcinomas, islet cell carcinomas, cystadenomas, cystadenocarcinomas, carcinoid tumors, duodenal carcinomas, distal bile duct, and ampullary carcinomas are not eligible.
- Evidence of distant metastasis on upright chest x-ray (CXR), computed tomography (CT) or other staging studies
- Subjects with recurrent disease

- Prior radiation therapy to the upper abdomen or liver
- .
- Subjects in their reproductive age group should use an effective method of birth control. Subjects who are breast-feeding, or have a positive pregnancy test will be excluded from the study
- Any co-morbidity or condition of sufficient severity to limit full compliance with the protocol per assessment by the investigator
- Concurrent serious infection
- Previous or current malignancies of other histologies within the last 5 years, with the exception of cervical carcinoma in situ, adequately treated basal cell or squamous cell carcinoma of the skin, and treated low-risk prostate cancer.

## 5.0 TREATMENT EVALUATION, ADMINISTRATION, AND MODIFICATION

### *SBRT guidelines*

#### *5.1 Tissue constraints*

Appropriate beam “nodes” or angles shall be selected to treat the primary site and areas at risk for occult disease spread. Careful target definition of these areas at risk is essential for optimal outcome. Beam shaping for treatment delivery shall be via conical or multi-leaf collimation (MLC). Treatment shall be via linear accelerator (LINAC) commissioned and equipped to deliver SBRT. Normal tissues and sensitive critical structures (e.g. duodenum, spinal cord, stomach, bowel, kidneys, liver, etc) shall be counteracted and the dose to these organs limited. See table below.

Normal Tissue Constraints	
Organ	Maximum Dose in 3 fractions
Liver (700 cm  )	15 Gy
1/3 of total kidney volume (left and right)	15 Gy
Spinal Cord	18 Gy
Stomach	30 Gy
Duodenum/small bowel	18 Gy

As discussed above the CTV will be equivalent to the PTV, unless the motion study reveals motion in the target volume. In that case, margins will be given to account for that motion.

#### *5.2 Dose Specification, Homogeneity Considerations & Plan Evaluation*

The treatment plan used shall be based on the assessment of the dose-volume histogram (DVH) with attention to coverage of the planning tumor volume (PTV) and critical normal structures.

The prescription dose is the isodose cloud that encompasses at least 95% of the PTV.

No more than 20% of any PTV shall receive doses >110% its prescribed dose

No more than 2% of any PTV shall receive <93% of its prescribed dose

No more than 5% of any normal tissue shall receive doses in excess of 110% of the primary PTV dose.

#### *5.3 On-Treatment assessment and post-treatment toxicity evaluation*

All subjects will be seen prior to delivery of each fraction of SBRT with toxicity evaluated by physical examination. Subsequently, subjects will be evaluated for toxicity 10-12 weeks later and then every 3 months until at least 2 years. Toxicities will be scored by the NCI CTC AE version 4.0. Also see Section 6.0.

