### 6.2 Evaluation during treatment

The subjects will be carefully followed while on active treatment and post-treatment for 24 months, or until death. Evaluation during treatment will consist of the following activities:

- 6.2.1 Administration of SBRT
- 6.2.3 Interim medical history and physical examination at baseline, prior to SBRT treatment, at the end of SBRT, and 10-12 weeks after SBRT then every 3 months thereafter for up to 24 months.
- 6.2.4 Serum chemistry and electrolytes to include BUN, creatinine, sodium, potassium, bicarbonate, chloride, calcium, magnesium, glucose, total bilirubin, AST, ALT, alkaline phosphatase post-treatment as clinically indicated
- 6.2.5 Hematologic studies to include CBC with differential and platelet count prior to SBRT and repeated 10-12 weeks later and then at follow-up as clinically indicated.
- 6.2.6 CT scan will be obtained at 10-12 weeks post-treatment and will be reviewed for evidence of response. Since these subjects will likely have no gross disease on imaging, the main goal of the follow-up scans is to monitor for local and distant progression as defined below.

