#### *6.4.5 Safety evaluation*

All patients will be monitored for potential treatment-related toxicity throughout treatment as detailed in the schema. Toxicity will be graded according to the CTCAE, which is further detailed in section 8.2.1. Acute toxicity is defined as toxicity occurring within 3 months of completion of SBRT. Late toxicity is defined as toxicity occurring greater than 3 months after treatment.

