#### 7.2.2 Rate of Accrual

We anticipate that 2 to 4 study-eligible patients will be enrolled per month. Thus, our planned study size of 50 patients to be enrolled within 24 months is well within our capacity.

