#### *7.4. Early Stopping for Toxicity*

Toxicity will be monitored continuously, with protocol amendment being made as needed. For safety, we will consider that regimen to be excessively toxic and stop accrual if, at any time, the observed rate of grade 3-5 acute or late toxicity as defined above in Section 6.4.5  $\geq 33\%$  and at least 4 toxicities have been observed.

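### No toxicity assessment is scheduled between the end of SBRT and 10-12 weeks, so 77-92% of the 3-month acute window rests on passive reporting and recall

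*Combined protocol and SAP*

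**What the plan says.** **During treatment.** Section 5.3: "All subjects will be seen prior to delivery of each fraction of SBRT with toxicity evaluated by physical examination". Section 6.2.3 adds a history and physical when SBRT finishes.

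**After treatment.** Section 5.3 continues: "Subsequently, subjects will be evaluated for toxicity 10-12 weeks later and then every 3 months until at least 2 years". Section 6.2.3 has the same spacing: "at the end of SBRT, and 10-12 weeks after SBRT then every 3 months thereafter for up to 24 months". The 6.3 table has no column between fraction 3 and 10-12 weeks.

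**Acute window.** Section 6.4.5: "Acute toxicity is defined as toxicity occurring within 3 months of completion of SBRT". Acute toxicity is part of secondary objective 2.5, and 7.3.3 plans to report its percentage with a 95% confidence interval.

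**Monitoring.** Section 7.4: "Toxicity will be monitored continuously, with protocol amendment being made as needed". The rule acts on "the observed rate of grade 3-5 acute or late toxicity as defined above in Section 6.4.5", at a threshold of 33% and once "at least 4 toxicities have been observed". Section 8.1 provides monthly toxicity review. Section 8.2 has every observed or volunteered adverse event recorded, and reportable serious events notified within 24 hours.

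**Accrual.** Section 7.2.2: "We anticipate that 2 to 4 study-eligible patients will be enrolled per month".

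**The concern.** The three fractions are given on alternate days, so scheduled contact ends soon after it begins. One visit, near the end of the 3-month window, is the only planned post-treatment assessment inside it. The short-term risks listed in 5.4 include nausea, vomiting, diarrhoea, abdominal pain and fatigue, which can arise and settle before week 10.

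Three results depend on catching them:

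- the acute toxicity percentage in 7.3.3, which would be too low if transient events go unrecorded;
- the tabulation by time of onset in 7.3.3, which is harder to interpret if systemic therapy has begun in the gap and dates are reconstructed afterwards;
- the stopping rule in 7.4, which is described as continuous but has no scheduled contact supplying it with data on a given patient during the gap.

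**Working it through.** The plan gives no operating characteristic for the toxicity rule, so there is no figure of its own to reproduce on this point. Its one computed figure, 94% power for LPFS in 7.2.1, does not enter here and would not change.

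**1. Share of the acute window with no scheduled assessment.** Inputs: 10-12 weeks (5.3, 6.2.3); 3 months (6.4.5); a month taken as 30.44 days.

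- Window: 3 × 30.44 = 91.3 days.
- Gap: 10 × 7 = 70 days to 12 × 7 = 84 days.
- Share: 70 / 91.3 = 77%; 84 / 91.3 = 92%.

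**2. Does another scheduled item fill the gap?**

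- FACT-G asks about the past 7 days (Appendix A), and the 6.3 table next places it at the 10-12 week visit. Section 6.4.4 also mentions a questionnaire after SBRT but gives no date.
- Blood counts are next due at 10-12 weeks. Post-treatment chemistry is done only when clinically indicated (6.2.4, 6.3 table), although liver function abnormality is a short-term risk in 5.4.
- The end-of-SBRT examination falls at or about the last fraction and does not shorten the gap materially.

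So detection in the gap is passive.

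**3. Patients enrolled during one gap.** Formula: monthly accrual × gap in days / 30.44.

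- 2 per month: 2 × 70 / 30.44 = 4.6; 2 × 84 / 30.44 = 5.5.
- 4 per month: 4 × 70 / 30.44 = 9.2; 4 × 84 / 30.44 = 11.0.

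That is about 5 to 11 patients, or 9% to 22% of 50.

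**4. What a reporting lag does to the stopping rule.** This is an illustration with 20,000 simulated trials per setting. Assumptions not in the documents: the true grade 3-5 rate; evenly spaced enrolment; every event unknown until the full lag has passed; and a rate calculated among patients whose lag has elapsed (7.4 does not define the denominator). Entries are the mean number enrolled when the rule is met, or 50 if it never is; ranges run from 2 to 4 patients per month.

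| True rate | Rule ever met | No lag | 1 month | 10 weeks | 12 weeks |
|---|---|---|---|---|---|
| 20% | 27% | 39.7 | 40.2-40.8 | 40.8-42.1 | 41.1-42.7 |
| 40% | 96% | 12.7 | 14.7-16.6 | 16.6-21.3 | 17.5-23.2 |
| 50% | 99.9% | 8.4 | 10.4-12.4 | 12.4-17.4 | 13.4-19.4 |

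The lag does not alter whether the rule is met, only how many patients have enrolled by then. At a 40% rate, cutting the lag from 10 weeks to 1 month saves 16.6 − 14.7 = 1.9 patients at 2 per month and 21.3 − 16.6 = 4.7 at 4 per month. This is an upper limit on the gain for that comparison, because many serious events would be known sooner and a check at about 4 weeks cannot find events that start later.

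**The case against.** The other side has a good case, and much of it stands.

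- **A reader might infer that the acute period is seen only by recall.** The documents do not support that. Section 8.2 has all observed or volunteered events recorded whenever they come to light.
- **A reader might infer that the stopping rule runs on data about 10 weeks old.** That is also too strong. The rule counts only grade 3-5 events, and 7.3.3 describes serious events as grade 3 or higher. If that wording governs reporting, a known event is notified within 24 hours and reaches the monthly review. Ten to twelve weeks is the longest delay, for an event that starts just after SBRT and that nobody reports; one starting midway through the gap is 5-6 weeks old at the visit. Once the trial is under way, earlier patients' visits also feed each review.
- **A reader might assume that systemic therapy has usually started by the 10-12 week visit.** Section 3.5 says only that the medical oncologist may give it, at his or her discretion.
- **The institution's own experience (1.3.1) is reassuring:** no grade 3-4 toxicity in 24 post-operative patients, and acute grade 3 toxicity in 3 of 71 patients (4%) with intact tumours. The 40% and 50% rows above lie far from this.
- **A call at about 4 weeks still leaves 6-8 weeks without contact** before the 10-12 week visit.

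What does not fall: 24-hour reporting starts only when someone knows of the event, and no contact is scheduled to find one. Section 8.2 also refers to external IRB criteria for what is reportable, so it is not certain that every grade 3 event counted by 7.4 is covered. Neither safeguard does much for lower-grade events, which belong in the acute toxicity percentage but not in the stopping rule.

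**Conclusion.** The concern holds in a limited form. No active toxicity assessment is scheduled for 70-84 of about 91 days (77-92%) of the acute window. Transient, mainly lower-grade acute events may therefore be under-counted in the 7.3.3 estimate, and onset is harder to place relative to any systemic therapy. The first part is plain from the schedule; the under-count is a reasoned expectation whose size the documents do not give. A figure can be produced only by assuming it: if a quarter to a half of events were missed, a true 20% would be reported as 20% × 0.75 = 15% down to 20% × 0.5 = 10%, but neither input is in the plan.

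For the stopping rule, the delay is at most 10-12 weeks, with about 5 to 11 further patients enrolled at 2-4 per month, and only for grade 3-5 events not reported earlier. The primary endpoint, sample size and power are unaffected. This is a worthwhile, inexpensive improvement to safety ascertainment and not a flaw that undermines the trial.

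**What to change.** Add to 5.3 and the 6.3 table one CTCAE v4.0 toxicity check at about 4 weeks after the last fraction. It can be a telephone call by existing study staff, or abstraction from a medical-oncology visit where one takes place. Record the date of the first systemic dose, alongside the event onset date that 7.3.3 already needs. State that the result enters the 7.4 count and the monthly review in 8.1.

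When editing these sections, reconcile the treatment week as well: 5.3 has toxicity evaluated before every fraction, whereas the 6.3 table marks history and physical only at fractions 1 and 3.

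The cost is about 50 short contacts or abstractions and one added date field, with no extra clinic visit, test or staff. The longest interval without contact in the acute window falls from 10-12 weeks to 6-8 weeks. The reported toxicity rate may be slightly higher because fewer events are missed.
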